5.3 Informed Consent

All subjects must have the ability to sign a written informed consent (see **Section 6.2** for informed consent process).

5.4 Inclusion of Women and Minorities

The study is open to patients of all races and ethnicities. However, given the cancer under study, only women will be recruited to the study.

6.0 Screening, Registration, and Follow-up Studies

6.1 Subject Identification and Recruitment

Patients with histologically-confirmed stage IV resistant metastatic TNBC will be identified and asked to participate in the study by the clinician. All patients will be recruited from patients undergoing treatment at City of Hope (COH).

Diagnostic or laboratory studies performed exclusively to determine eligibility for this trial will be performed only after obtaining written informed consent (see **Section 6.2**). Studies or procedures performed for clinical indications (not exclusively to determine study eligibility) may be used for baseline values, even if the studies were done before informed consent was obtained (see **Study Calendar** for further details of study-related tests; **Section 6.4**).

6.2 Informed Consent Process

Patients will be given copies of the consent form and the patient bill of rights to review and sign if they consent to participate in the study. The Principal Investigator or Co-Investigators will explain the nature, duration, purpose of the study, potential risks, alternatives, and potential benefits, and all other information contained in the informed consent document. In addition, they will review the experimental subject's bill of rights and the Health Insurance Portability and Accountability Act (HIPAA) research authorization form. Research subjects will be informed that they may withdraw from the study at any time and for any reason without prejudice, including as applicable, their current or future care or employment at COH or any relationship they have with COH. General questions will be answered by the Principal Investigator and Co-Investigators, and more complex questions requiring a medical opinion will be answered by the Principal Investigator and Co-Investigator physicians.

Should sufficient doubt be raised regarding the adequacy of comprehension, further clarifications will be made and the questionnaire repeated until a satisfactory result is obtained. Prospective research subjects who cannot adequately comprehend the fundamental aspects of the research study with a reasonable amount of discussion, education, and proctoring will be ineligible for enrollment.

6.3 Dose Level Assignment

Dose level will be assigned as described in **Section 11**.

6.4 Study Calendar

ERIBULIN/EVEROLIMUS SCHEDULE Q21 DAYS

	Cycle 1										Cycle 2 +									
	Off Studyi					Day 1 through 21.....→					←Continuous Day 1 through 21.....→					Continuous Day 1 through 21.....→				
Everolimus																				
Eribulin ^a																				
Informed consent	X																			
Demographics	X																			
Medical history	X																			
Height	X																			
EKG ^b	X																			
B-HCG ^c	X																			
Con-Meds	X																			
Everolimus dose diary	X																			
Physical exam	X	X																		
Vital signs	X	X																		
Weight	X	X																		
Performance status	X	X																		
CBC w/diff, pts	X	X																		
Serum chemistry ^d	X	X																		
Tumor Biopsy ⁱ	X	X																		
Skin Punch Biopsy ^e	X	X																		
Blood/Correlative ^h	X	X																		
Pharmacokinetics ^f		X	X																	
Adverse events																				
Tumor measurements	X																			
Radiologic	X																			

^aTumor measurements are repeated every 2 cycles (~6 weeks). Documentation (radiologic) must be provided for patients removed
^bFrom study for progressive disease.
^cRadiologic measurements are repeated every 2 cycles (~6 weeks).

evaluation ^g	
-------------------------	--

a: Actual body weight will be used for BSA and Eribulin dose calculation. **b:** Pre-study and every two cycles. **c:** Serum pregnancy test (women of childbearing potential). **d:** Albumin, alkaline phosphatase, total bilirubin, bicarbonate, BUN, calcium, chloride, creatinine, glucose, LDH, phosphorus, potassium, magnesium, total protein, SGOT [AST], SGPT [ALT], sodium. **e:** Two sets of punch biopsies (two biopsies per set for a total of four biopsies – Optional for patients who consented at RP2D level) will be performed as follows: First set- Biopsy 1 will be performed one week prior to any dosing (pre-study). Biopsy 2 will be performed on the same site as Biopsy 1 on the day of the first dose of eribulin and everolimus; cycle 1 (prior to any dosing). Second set: Biopsy 3 will be performed on a new site on the day that the second dose of eribulin is given (prior to dosing). **f:** To be performed in a subset of patients enrolled on the Phase Ib portion of the study (see section 12.0). **g:** Staging images (CT scans, bone scan) must be performed within 28 days prior to study entry. **h:** Blood correlative studies will be collected pre-study, before the first dose of everolimus and eribulin, at 4 and 8 hours after the first dose of everolimus and eribulin on day 1, and at two post-dose time points on days 4 and 8 of the first cycle for patients on the expanded cohort of RP2D. **i:** Mandatory tumor biopsy specimen (fresh frozen and/or paraffin-embedded) will be obtained prior to study entry. An optional tumor tissue biopsy will be obtained upon disease progression. **j:** Pre-study assessments should be performed within 28 days prior to initiating therapy, unless otherwise noted. For the on-study treatment, there is a +/- 3 days of window allowed.

Items e, f, h: ONLY for patients enrolled to the expanded cohort, i.e. RP2D.

6.5 Registration Guidelines

General Guidelines

Eligible patients will be registered on the study centrally at the Data Coordinating Center (DCC) at the City of Hope. Staff (including physicians, protocol nurses and/or CRAs) should call the DCC at [contact], [name] to verify dose level and slot availability, and to reserve a slot for a specific prospective subject. Slots can only be held for a limited time as specified in Appendix C.

Eligible patients must be registered within 2 weeks prior to start of protocol therapy.

Issues that would cause treatment delays should be discussed with the Principal Investigator. If a patient does not receive protocol therapy following registration, the patient's registration on the study may be canceled. The Data Coordinating Center should be notified of cancellations as soon as possible.

Registration Process

Once a slot at a dose level has been reserved, the signed informed consent has been obtained, all pretreatment evaluations have been performed, and patient's eligibility has been confirmed by the Data Coordinating Center, a patient will be registered on study.

To register a patient, the treating physician should contact the protocol nurse or the responsible Clinical Research Associate (CRA) in Clinical Trial Office (CTO) to complete the eligibility/registration form. The protocol nurse or CRA will contact the Data Coordinating Center at the City of Hope [contact], [name] or e-mail [contact]), EMAIL a copy of the completed eligibility checklist, required pre-study tests (per protocol – and may include laboratory, CT and pathology reports), signed Informed Consent, signed Patients' Bill of Rights and HIPAA authorization form to [contact]. See Appendix C ("Registration Procedures").

The protocol nurse or CRA will then call the Data Coordinating Center ([name]) to confirm receipt of all registration documents. To complete the registration process, the Data Coordinating Center will:

- Verify and confirm the patient's eligibility.
- Assign a patient accession number (for example, COH-001, COH-002, etc.).
- Register the patient on study centrally (the City of Hope CRA assigned to the trial will still be responsible for accessioning via MIDAS). If multi-site study, COH DCC staff will be responsible for registering the participating site patients at City of Hope.
- Assign the patient to a dose level (as applicable).
- Complete and email a Confirmation of Registration form within 24 hours to include the COH patient study number and dose level (as applicable) to the study team, which will include the Principal Investigator, treating physician, protocol nurse, CRA and COH IDS Pharmacy.
- Call the protocol nurse and/or CRA to verbally confirm registration.
- A patient failing to meet all protocol requirements will not be registered.

7.0 Study Treatment Protocol

7.1 Eribulin mesylate (E7389)

7.1.1 Nomenclature

Chemical Name (USAN/INN):

(2R,3R,3aS,7R,8aS,9S,10aR,11S,12R,13aR,13bS,15S,18S,21S,24S,26R,28R,29aS)-2-[(2S)-3-Amino-2-hydroxypropyl]-3-methoxy-26-methyl-20,27-dimethylidenehexacosahydro-11,15:18,21:24,28-triepoxy-7,9-ethano-12,15-methano-9H,15H-furo[3,2-i]furo[2',3':5,6]pyrano[4,3-b][1,4]dioxacyclopentacosin-5(4H)-one methanesulfonate (salt).

7.1.2 Chemical and structural formula

Molecular formula: C41H63NO14S (C40H59NO11 · CH4O3S).

Molecular weight: 826.00.

7.1.3 Physical and chemical characteristics

Appearance: White powder.

Hygroscopicity: Eribulin is hygroscopic.

7.1.4 Description

Eribulin currently used in clinical studies contains 1.0mg drug substance in 2.0mL of solution. Eribulin rug product is a clear, colorless, and sterile solution packaged in a glass vial.

7.1.5 Storage

The long-term storage condition for commercial Eribulin is 25°C (do not freeze). Investigational labeled Eribulin is stored in the refrigerator at 2-8 °C. .

7.1.6 Dosage

The drug product will provided by Eisai for this trial. It will be administered per Eisai's directions without dilution or diluted in up to 100mL 0.9% sodium chloride (for injection). Do not dilute in or administer through an intravenous line containing solutions with dextrose.

7.2 Everolimus

7.2.1 Nomenclature

Chemical name: (1R,9S,12S,15R,16E,18R,19R,21R,23S,24E,26E,28E,30S,32S,35R) - 1,18-dihydroxy-12-[1]-19,30-dimethoxy15,17,21,23,29,35-hexamethyl-11,36-dioxa-4-azatricyclo[30.3.1.04,9]hexatriaconta-16,24, 26,28-tetraene-2,3,10,14,20pentaone

7.2.2 Chemical and structural formula

Molecular formula: C53H83NO14.

Molecular weight: 958.2.

7.2.3 Physical and chemical characteristics

Appearance: White to faintly yellow powder.

7.2.4 Description

Everolimus stabilized with butylated hydroxytoluene (BHT) is amorphous, and contains 0.2% BHT as an antioxidant. The drug substance, everolimus, contains 15 asymmetric carbon atoms and 4 substituted double bonds. The configuration of the asymmetric carbon atoms and the double bonds are guaranteed by the microbial origin of rapamycin, the starting material of the synthesis, and by the X-ray analysis performed on crystalline everolimus. The configuration at carbon 40 is not changed by the chemical derivatization that converts rapamycin into everolimus.

7.2.5 Storage

Stability: Shelf-life of 36 months when stored at <30°C. Protect from light and moisture.

7.2.6 Dosage

2.5mg and 5mg tablets will be provided by Novartis for this trial. Everolimus should be administered orally, once daily at the same time every day either consistently with food or consistently without food. Tablets should be swallowed whole with a glass of water. The tablets must not be chewed or crushed. For patients unable to swallow tablets, everolimus tablet(s) should be dispersed completely in a glass of water (containing approximately 30mL) by gently stirring, immediately prior to drinking. The glass should be rinsed with the same volume of water and the rinse should be completely swallowed to ensure that the entire dose is administered.

7.3 Treatment Overview

For a tabular view of the treatment, monitoring, and follow-up schedule, see **study calendar** in **Section 6.4**. For dose levels see the study design (**Section 4.0**).

7.4 Planned Duration of Therapy

Treatment cycle length is 21 days with response evaluation every 2 cycles.

7.5 Subject Follow-Up

Patients will be followed after removal from study until death. Patients removed from study for AEs will be followed until resolution or stabilization of the AE (See **Section 10** for further AE information).

7.6 Supportive Care, Other Concomitant Therapy, Prohibited Medications

Ondansetron will be used as pre-medication for prophylaxis of eribulin induced nausea. If needed, prior to each treatment with eribulin, patients may be pre-medicated with dexamethasone 10mg to prevent a hypersensitivity reaction. Ondansetron 8mg oral tablet will be used as needed at home for treatment related nausea and/or vomiting.

7.6.1 Dexamethasone Mouth Wash

To reduce dose-limiting oral mucositis, a **mandatory dexamethasone mouth wash (alcohol-free 0.5 mg/5 mL dexamethasone solution) will be used for primary prophylaxis of oral mucositis**. Patients will start the prophylactic oral care regimen on the same day they start treatment with everolimus + eribulin. The mouthwash should be taken as directed in section **8.1.2**. Treating physician or other health provider of the treatment team will write the prescription of the steroid-based mouthwash. Usage of the mouth wash should be documented by patient and followed up during clinic visit. After first two cycles of treatment, patient can use the steroid mouth wash 4 times a day as needed .

7.6.2 Concomitant medications

Patients must be instructed not to take any medications (over-the-counter or other products) during the protocol treatment period without prior consultation with the investigator. The investigator should instruct the patient to notify the study site about any new medications he/she takes after the start of study drug. All medications (other than study drug) and significant non-drug therapies (including physical therapy and blood transfusions) taken within 28 days of starting study treatment through the 30-day safety follow up visit should be reported on the CRF.

7.6.2.1 Angioedema with concomitant use of angiotensin-converting enzyme (ACE) inhibitors

Patients taking concomitant ACE inhibitor therapy may be at increased risk for angioedema (e.g. swelling of the airways or tongue, with or without respiratory impairment).

7.6.2.2 Cytochrome P450 and P-glycoprotein inhibitors/inducers/substrates

Everolimus is metabolized by CYP3A4 in the liver and to some extent in the intestinal wall. Inhibitors of CYP3A4 or PgP may cause increased everolimus concentrations. Inducers of CYP3A4 or PgP may cause decreased everolimus concentrations. Everolimus is a substrate of CYP3A4, and a substrate and moderate inhibitor of the multidrug efflux pump, PgP (PgP, MDR1, and ABCB1). The extent of absorption and subsequent elimination of systemically absorbed everolimus may be influenced by products that are substrates, inhibitors, or inducers of CYP3A4 and/or PgP. In vitro studies showed that everolimus is a competitive inhibitor of CYP3A4 and of CYP2D6, potentially increasing the concentrations of products eliminated by these enzymes.

Therefore,

- Co-administration with strong inhibitors of CYP3A4 or with a P-glycoprotein (PgP) inhibitor is not permitted.
- Coadministration with PgP substrates should be with caution as everolimus can affect their drug concentrations.
- Co-administration with moderate CYP3A4 inhibitors is not permitted. If a patient requires co-administration of moderate CYP3A4 inhibitors, everolimus therapy must be interrupted. Once the inhibitor is discontinued, everolimus can be resumed only after discussion with the PI and after a minimum washout period of 2 days (or longer depending on agent's half life).
- Grapefruit, Seville oranges, and starfruit affect P450 and PgP activity. Concomitant use is not permitted.

- Coadministration of a CYP3A4 inducer is not permitted except topical steroid. Oral dexamethasone mouth wash is allowed.
- Coadministration with CYP3A4 and CYP2D6 substrates should be done with caution.

For a current table of Substrates, Inhibitors and Inducers please access the following website:

<http://www.fda.gov/Drugs/DevelopmentApprovalProcess/DevelopmentResources/DrugInteractionsLabeling/ucm093664.htm>.

Please refer to the tables below listing relevant inducers and inhibitors of CYP3A and for a list of relevant substrates, inducers, and inhibitors of PgP.

Clinically relevant drug interactions: inducers, and inhibitors of isoenzyme CYP3A

Inducers

mitotane, genistein, thioridazine, bexarotene, clobazam, danshen, Echinacea, garlic (allium sativum), ginkgo (ginkgo biloba), glycyrrhizin, methylprednisolone, primidone, raltegravir, sorafenib, telaprevir, terbinafine, carbamazepine, glucocorticoids, modafinil, oxcarbazepine, phenobarbital, phenytoin, pioglitazone, rifabutin, rifampin, St. John's wort, troglitazone, efavirenz, nevirapine, topiramate, avasimibe, bosentan, etravirine, naftcillin, ritonavir, talviraline (not available in US market), tipranavir, amprenavir, aprepitant, armodafinil (R-modafinil), dexamethasone*, nevirapine, prednisone, pleconaril (not available in US market), rufinamide

Inhibitors

Strong inhibitors:

Boceprevir, cobicistat, telaprevir, clarithromycin, conivaptan, indinavir, itraconazole, ketoconazole, lopinavir, mibefradil, nefazodone, neflifinavir, ritonavir, saquinavir, telithromycin, troleandomycin, voriconazole, tipranavir, elvitegravir, posaconazole.

Moderate inhibitors:

Aprenavir, cyclosporine, schisandra sphenanthera, aprepitant, atazanavir, casopitant, cimetidine, ciprofloxacin, darunavir, diltiazem, erythromycin, fluconazole, grapefruit juice (citrus paradisi fruit juice), imatinib, tofisopam, verapamil, amprenavir, fosamprenavir, dronedarone.

***Topical steroid such as oral dexamethasone mouth wash is allowed.**

Clinically relevant drug interactions: substrates, inducers, inhibitors of PgP and PgP/CYP3A dual inhibitors

Substrates

Talinolol, everolimus, digoxin, fexofenadine, indinavir, vincristine, colchicine, topotecan, paclitaxel

Inducers

rifampin, St John's wort

PgP Inhibitors and PgP/CYP3A Dual Inhibitors

Azithromycin, fluvoxamine, nelfinavir, paroxetine, amiodarone, captopril, carvedilol, clarithromycin, conivaptan, diltiazem, dronedarone, elacridar, erythromycin, felodipine, fexofenadine, ginkgo (ginkgo biloba), indinavir, itraconazole, , lopinavir, mibefradil, milk thistle (silybum marianum), nifedipine, nitrendipine, quercetin, quinidine, ranolazine, ritonavir, saquinavir, schisandra chinensis, St John's wort (hypericum perforatum), talinolol, telmisartan, tipranavir, valsartan, verapamil.

Reference: Internal Clinical Pharmacology Drug-drug interaction (DDI) memo, updated Oct. 2, 2011, which summarizes DDI data from three sources including the FDA's "Guidance for Industry, Drug Interaction Studies", the University of Washington's Drug Interaction Database, and Indiana University School of Medicine's Drug Interaction Table.

7.6.3 Vaccinations

Immunosuppressants may affect the response to vaccination and vaccination during treatment with everolimus may therefore be less effective. The use of live vaccines should be avoided during treatment with everolimus. Examples of live vaccines are: intranasal influenza, measles, mumps, rubella, oral polio, BCG, yellow fever, varicella, and TY21a typhoid vaccines.

8.0 Dose Delays/Modifications

8.1 Everolimus

The most common AEs reported for everolimus that may require dose modifications are stomatitis, rash, and non-infectious pneumonitis.³⁰

8.1.1 Dose Limiting Toxicities

Definition of dose limiting toxicities (DLTs) based on CTCAE 4.0. All toxicities will be attributed to study drug (everolimus) except hematological toxicities. Hematological DLTs will be defined for the combination of eribulin and everolimus. If a hematological DLT occurs, dose reduction or delay will be conducted according to rules defined in 8.1.6 and 8.2.2.

DLT is defined as an AE or abnormal laboratory value as at least possibly related to the study medication and meets any of the criteria per CTCAE 4.0 . The following table is recommended for the most anticipated toxicities.

Decisions to escalate, de-escalate, or expand a dose level will be based on the first course of treatment. To be evaluable for toxicity, a patient must receive at least 1 complete course of treatment (at least 75% of planned dose of both drugs without toxicity) and be followed for at least 21 days (more if there is a dose delay) or have experienced a DLT as defined above. All patients enrolled are to be fully followed for toxicity; any patients who

are not evaluable for toxicity will be replaced. Intra-patient dose escalation is not allowed.

Table 8.1.1a Criteria for defining dose-limiting toxicities.

Toxicity	DLT criteria
Hematology	CTCAE grade ≥ 3 neutropenia lasting more than 7 consecutive days
	CTCAE grade 4 thrombocytopenia
	CTCAE grade 4 neutropenia
	CTCAE Grade 3 neutropenia with fever (temperature $\geq 38.5^{\circ}\text{C}$)
Non-hematology	Any CTCAE grade ≥ 3 AEs with the following exceptions
Exceptions to DLT criteria	Grade 3 alopecia
	Controllable grade 3 nausea and vomiting
	<5 days of CTCAE grade 3 fatigue
	Triglycerides $< 1,500\text{mg/dL}$, which recover within 1 week
	Grade 3 laboratory abnormalities that are correctable to grade 2 or less within 24 hours
	Grade 3 hyperglycemia that is controlled to Grade 2 and under should not be considered DLT. For management of hyperglycemia, please refer to section 8.1.9.
Treatment delays	>2 weeks as a result of unresolved toxicity during the first cycle of therapy (failure of ANC to recover to $\geq 1,000/\mu\text{L}$ or platelets to recover to $\geq 50,000/\mu\text{L}$ within 14 days of the last treatment)
Others	Failure to complete at least 75% of planned dose of either one of the drugs during cycle 1, due to toxicity, will also be considered a DLT.

Follow-up for toxicities.

Patients whose treatment is interrupted or permanently discontinued due to an AE or clinically significant laboratory value, must be followed up weekly (or more frequently if clinically indicated) for 4 weeks, and subsequently at approximately 4 week intervals, until resolution or stabilization of the event, whichever comes first. Appropriate clinical experts such as cardiologist, pulmonologists etc should be consulted as deemed necessary. All patients must be followed up for 21 days when taken off study.

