8.2 Eribulin

8.2.1 Dose delays during therapy

Do not administer eribulin mesylate on Day 1 or Day 8 for any of the following:

- ANC $<1 \times 10^9/L$
- PLT $<75 \times 10^9/L$
- Grade 3 or 4 non-hematological toxicities attributed by eribulin.

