8.2.2 Dose adjustment during therapy

Subjects should be clinically evaluated during treatment by physical examination and laboratory testing including complete blood counts as indicated per protocol (see **Section 6.4**). If Grade 3 and 4 toxicities are present, treatment should be delayed to allow recovery. Subjects should only be retreated when ANC is $\geq 1 \times 10^9/L$ and PLT are $\geq 75 \times 10^9/L$ and all other toxicity from a previous cycle has recovered to \leq Grade 2.

Recommended dose reductions as indicated in the US Package Insert are as follows:

Permanently reduce the $1.4 \text{mg}/\text{m}^2$ eribulin mesylate dose to $1.1 \text{mg}/\text{m}^2$ for any of the following:

- ANC $<500 \text{ mm}^3$ for >7 days.
- ANC $<1,000 \text{ mm}^3$ with fever or infection.
- Platelets $<25,000 \text{ mm}^3$.
- Platelets $<50,000 \text{ mm}^3$ requiring transfusion.
- Non-hematologic Grade 3 or 4 toxicities graded according to NCI CTCAE v4.0.
- Omission or delay of Day 8 dose in previous cycle for toxicity.

Furthermore:

- If any event requires permanent dose reduction while receiving $1.1 \text{mg}/\text{m}^2$, reduce the dose to $0.7 \text{mg}/\text{m}^2$.
- If any event requires permanent dose reduction while receiving $0.7 \text{mg}/\text{m}^2$, discontinue eribulin.

There will be no dose reductions outside of the scheduled physical examination and laboratory testing including complete blood counts indicated per protocol (see Section 6.4).

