10.7.1 Eribulin

The most common AEs reported in >1 of 10 subjects receiving eribulin are shown below based on 827 breast cancer subjects who received the recommended dose in Phase II and Phase III breast cancer studies.

AE	Adverse Reactions (all grades)
Blood and Lymphatic System Disorders	
Neutropenia	54.5%
Leucopenia	22.1%
Anemia	20.3%
Nervous system disorders	
Peripheral neuropathy	32%
Headache	11%
Asthenia/Fatigue	52.8%
Mucosal inflammation	9.8%
Pyrexia	16.6%
Gastrointestinal disorders	
Constipation	16.3%
Diarrhea	15.0%
Nausea	35.1%
Vomiting	14.5%
Musculoskeletal and connective tissue disorders	
Arthralgia/Myalgia	12.7%
Back pain	1.9%
Bone pain	1.7%
Pain in extremity	4.7%
Investigations	
Weight decreased	9.7%
Metabolism and nutrition disorders	
Decreased Appetite	18.5%
Respiratory, thoracic, and mediastinal disorders	
Cough	4.7%
Dyspnea	5.6%
Skin and subcutaneous tissue disorders	
Alopecia	49.7%
Infections and Infestations	
Urinary Tract Infection	4.8%

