10.8 Other AE Factors to Consider

Factors to be considered in assessing the relationship of the AE to study drugs include:

- *The Temporal Sequence from Drug Administration:* The event should occur after the drug is given. The length of time from drug exposure to event should be evaluated in the clinical context of the event.
- *Recovery on Discontinuation (de-challenge), Recurrence on Reintroduction (re-challenge):* Subject's response after drug discontinuation (de-challenge) or subjects response after drug re-introduction (re-challenge) should be considered in the view of the usual clinical course of the event in question.
- *Underlying, Concomitant, Current Diseases:* Each report should be evaluated in the context of the natural history and course of the disease being treated and any other disease the subject may have.
- *Concomitant Medication or Treatment:* The other drugs the subject is taking or the treatment the subject receives should be examined to determine whether any of them may be suspected to cause the event in question.
- *The Pharmacology and Pharmacokinetics of the Test Drug:* The pharmacokinetic properties (absorption, distribution, metabolism and excretion) of the test drug(s), coupled with the individual subject's pharmacodynamics should be considered.

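### Sections 8.1.1, 8.1.5, 8.2.1 and 8.2.2 set inconsistent attribution conditions and instructions for grade 3-4 non-hematologic toxicity

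*Combined protocol and SAP*

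**What the plan says.** Section 8.1.1 (Dose Limiting Toxicities), under the heading for everolimus in Section 8.0, fixes attribution in advance: "All toxicities will be attributed to study drug (everolimus) except hematological toxicities". It then directs only the hematologic events onward: "If a hematological DLT occurs, dose reduction or delay will be conducted according to rules defined in 8.1.6 and 8.2.2". The same section also sets a relatedness test for each event: "DLT is defined as an AE or abnormal laboratory value as at least possibly related to the study medication".

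Section 8.2.1 opens "Do not administer eribulin mesylate on Day 1 or Day 8 for any of the following" and lists three triggers: a neutrophil threshold, a platelet threshold, and "Grade 3 or 4 non-hematological toxicities attributed by eribulin". Section 8.2.2 delays treatment when grade 3 or 4 toxicity is present. Among its reasons for permanent eribulin reduction it lists "Non-hematologic Grade 3 or 4 toxicities graded according to NCI CTCAE v4.0". Neither 8.2.2 rule mentions attribution.

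Section 8.1.5, for everolimus-related non-hematologic toxicity, interrupts everolimus for a grade 3 event (lipid and glucose exceptions apart). It withdraws the patient from the study if there is no recovery to grade 1 or less, or baseline, within 28 days. A later row of the same table, for interruptions longer than 28 days, discontinues everolimus and does not mention withdrawal.

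On causality, Section 10.6 has the relationship to investigational product recorded for each event. Section 10.8 begins "Factors to be considered in assessing the relationship of the AE to study drugs include" and lists matters to weigh case by case.

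**The concern.** Two drugs are given together, and the rules for holding, reducing or stopping each one depend on what caused the event. One section settles the cause for a whole class of events. A second makes the cause decisive, a third ignores it, and a fourth applies the consequences to the other drug. A physician could follow any one of these sections faithfully and act differently from a colleague who followed another.

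At stake are consistent handling of severe non-hematologic events, the dose of each drug actually delivered, and whether a patient leaves the study. The fixed attribution also disagrees with the protocol's own safety information: 10.7.1 lists reactions for eribulin that 10.7.2 does not list for everolimus.

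**Working it through.** There is no stated figure to reproduce; the main check is a side-by-side reading.

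**1. The rules for a grade 3 non-hematologic event**

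| Section | Attribution condition | Drug | Instruction |
|---|---|---|---|
| 8.1.1 | Fixed: everolimus | – | Sends only hematologic DLTs to 8.1.6 and 8.2.2 |
| 8.1.5, grade 3 row | Everolimus-related | Everolimus | Interrupt; withdraw from study if not at grade ≤1 or baseline within 28 days |
| 8.1.5, later row | Everolimus-related | Everolimus | Interruption over 28 days: discontinue everolimus |
| 8.2.1, third trigger | Must be attributed to eribulin | Eribulin | Do not give on day 1 or day 8 |
| 8.2.2 | None | Eribulin | Delay; retreat when other toxicity is grade ≤2; reduce permanently |

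If 8.1.1 governs, no non-hematologic event can be attributed to eribulin, so the third trigger of 8.2.1 is unreachable. Its neutrophil and platelet triggers do not use attribution and stand.

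**2. Example: grade 3 peripheral neuropathy on day 8**
- 8.1.1 assigns it to everolimus, and 8.1.5 interrupts everolimus.
- The attribution trigger of 8.2.1 is not met, but 8.2.2 delays and reduces eribulin.
- Suppose it settles at grade 2, above baseline, and is still there at 28 days. 8.2.2 permits eribulin retreatment if counts allow. The grade 3 row of 8.1.5 withdraws the patient from the study. The later row discontinues everolimus only.

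**3. An event type already seen.** Section 11.1.1 reports a grade 3 mucositis DLT at dose level 1. Under 8.1.1 it belongs to everolimus, and the stomatitis table in 8.1.2 adjusts everolimus only. Read literally, 8.2.2 also reduces eribulin permanently. The documents do not say what was done.

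**4. The toxicity lists.** For eribulin, 10.7.1 gives peripheral neuropathy 32% and constipation 16.3%, all grades, in 827 subjects; Section 1.2.1 gives neuropathy 34.6% in the phase 3 trial. Neither reaction appears in the 10.7.2 lists for everolimus.

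**5. How often the conflict could arise.** The triggers are grade 3-4, and the documents give no grade 3-4 rate for reactions listed only for eribulin. For an assumed rate p per patient, the chance of at least one case among n patients is 1 − (1 − p)^n; for example, 1 − 0.99^27 = 0.238.

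| Assumed p | n = 27 (at the RP2D) | n = 45 (planned maximum) |
|---|---|---|
| 1% | 24% | 36% |
| 2% | 42% | 60% |
| 5% | 75% | 90% |
| 10% | 94% | 99% |

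**6. Dose finding.** The reported DLT counts are the same whichever drug is named. Level 1 had 2 neutropenia + 2 mucositis = 4, and 4/8 = 50%. Level 2 had 2/3 = 67%. Both match Section 11.1.1. The TEQR and Simon rules use counts of patients, not causal drug.

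**The case against.** The best defense is that the 8.1.1 sentence belongs to the DLT definition and serves only to classify DLTs. Section 8.2.1 speaks of toxicity attributed to eribulin and so presupposes that it exists; confining 8.1.1 to DLT classification gives both sections effect. That reading is possible, but the text does not state it. The sentence stands in the section on dose delays and modifications, and its own paragraph goes on to dose reduction and delay. Even if the reading is granted, 8.2.1 still makes attribution decisive where 8.2.2 ignores it, and the sentence still clashes with 10.8 and the 10.7 lists.

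A second defense is that 8.2.2 largely covers the gap. This mostly stands: eribulin is delayed and reduced under 8.2.2 in the neuropathy example, and the silence of 8.2.1 is not an instruction to give the drug. It does not reconcile the two sections, and 8.1.1 sends no non-hematologic DLT to 8.2.2.

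A reader might also infer more than the documents support:
- That the whole eribulin hold is disabled. Only one of three triggers is affected.
- That the wrong drug would be stopped. Which drug should be held is a clinical judgement that the documents do not settle.
- That the toxicity-profile endpoint would assign eribulin reactions to everolimus. Section 11.3 tabulates by dose, course, organ and severity, not by causal drug.
- That sites would diverge. Section 14.7 makes this a single-center study, so any difference is between treating physicians.
- That the high rates of fatigue (52.8%) and nausea (35.1%) for eribulin measure the problem. These are all-grade figures, and 10.7.2 lists both reactions as very common with everolimus.

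**Conclusion.** The concern holds as an internal inconsistency that bears on patient safety. For grade 3-4 non-hematologic toxicity, the four sections set different attribution conditions and lead to different actions on each drug, and 8.1.5 also gives two outcomes at 28 days. That the third trigger of 8.2.1 cannot be reached depends on reading 8.1.1 literally and beyond DLT classification. The disagreement between 8.2.1 and 8.2.2 does not depend on that reading.

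The frequency cannot be estimated from the documents; the probabilities above rest wholly on assumed rates. The point gives no reason to revisit the DLT counts, the TEQR decisions or the Simon design.

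**What to change.** 1. State the scope of the attribution sentence in 8.1.1, for example that it serves DLT classification only.
2. Record relatedness to everolimus and to eribulin separately on the existing adverse event form, in line with 10.6 and 10.8.
3. Reconcile 8.1.1, 8.1.5, 8.2.1 and 8.2.2, including the two 28-day rows of 8.1.5, so that one event gives one consistent instruction per drug.

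Which clinical rule applies is for the sponsor to decide. The cost is amendment wording and one relatedness field per drug on an existing form. No sample size, decision boundary or planned analysis changes.
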